4.2 Scientific Rationale for Study Design

This study is designed to investigate the potential effect of tezepelumab on the antibody response to the quadrivalent seasonal influenza virus vaccine in participants 12 to 21 years of

age with moderate to severe asthma (see Section 2.1).

4.3 Justification for Dose

The selection of the 210 mg SC Q4W dose was based on efficacy and safety results from the Phase 2b PATHWAY study. In PATHWAY, 210 mg tezepelumab Q4W led to numerically improved efficacy compared with 70 mg Q4W, whereas the 280 mg Q2W dose did not increase efficacy further with the 210 mg Q4W dose. Tezepelumab was well-tolerated at all 3 doses and the safety profile was well balanced between the tezepelumab and placebo groups with no evidence of a dose relationship to AEs. Efficacy and safety of the 210 mg SC Q4W dose was further confirmed in the Phase 3 NAVIGATOR study in adults and adolescents with severe asthma.

4.4 End of Study Definition

A participant is considered to have completed the study if he/she has completed all visits of the study including the End of Study Visit or the last scheduled procedure shown in the SoA.

The end of the study is defined as the date of the last visit of the last participant in the study or last scheduled procedure for the last participant in the study.

5 STUDY POPULATION

Prospective approval of CSP deviations to recruitment and enrollment criteria, also known as CSP waivers or exemptions, is not permitted.

5.1 Inclusion Criteria

5.1.1 Study Eligibility

Participants are eligible to be included in the study only if **all** of the following criteria apply:

Informed Consent

- 1 Capable of giving signed informed consent/assent as described in [Appendix C](#) which includes compliance with the requirements and restrictions listed in the ICF/assent and in this CSP.

Age

- 2 Participant must be 12 to 21 years of age inclusive, at the time of signing the ICF/assent.

Type of Participant and Disease Characteristics

- 3 Documented physician-diagnosed asthma for at least 12 months prior to Visit 1.
- 4 Evidence of asthma as documented by either:
 - Post-bronchodilator airway reversibility ($FEV_1 \geq 12\%$ and ≥ 200 mL) demonstrated at Visit 1 or Visit 2 using the Maximum Post-bronchodilator Procedure.

OR

- Airway reversibility documented in the previous 12 months prior to Visit 1.

Note: All participants must have reversibility testing performed before randomization to establish a baseline characteristic even if historical documentation is used to meet this criterion.

- 5 Documented history of stable treatment with ICS and LABA for at least 30 days prior to Visit 1.
 - The ICS and LABA can be parts of a combination product or given by separate inhalers. For ICS/LABA combination preparations, both the mid and high-strength maintenance doses approved in the USA will meet this ICS criterion.
 - The ICS dose must be > 250 µg fluticasone propionate dry powder inhaler or equivalent daily. Equivalent ICS doses as detailed in [Appendix H](#).
 - Additional asthma controller medications (eg, LTRAs, short and long-acting anti-muscarinics, theophylline, oral corticosteroids, etc) that have been used for at least 30 days prior to Visit 1 are allowed.
- 6 Morning pre-bronchodilator FEV₁ of > 50% predicted normal value at Visit 1 or Visit 2.

Weight

- 7 Body weight ≥ 40 kg.

Sex

- 8 Male and female participants.

Contraceptive use by women of childbearing potential should be consistent with local regulations regarding the methods of contraception for those participating in clinical studies (see Section [5.3.4](#)).

5.1.2 At Randomization

Participants are eligible to be randomized if all of the following criteria apply:

- 1 For women of childbearing potential, a negative urine pregnancy test is required prior to administration of study intervention at Visit 3 (randomization).
- 2 Must have 'not well-controlled' asthma as documented by either:
 - **CCI** [REDACTED]
or
 - A peak expiratory flow of 60-80% predicted.
or
 - An exacerbation, one or more, that required oral corticosteroids in the previous 12 months.
or

- Any one of the following assessed by a participant recall over the previous 2-4 weeks:
 - Asthma symptoms > 2 days/week.
 - Night-time awakenings once or more per week.
 - SABA use for symptom control (not for the prevention of exercise-induced asthma) > 2 days/week.

NOTE: A participant's verbal history suggestive of asthma symptoms, but without supporting documentation, is not sufficient to satisfy these inclusion criteria.

5.2 Exclusion Criteria

5.2.1 Study Eligibility

Participants are excluded from the study if any of the following criteria apply:

Medical Conditions

- 1 Clinically important pulmonary disease other than asthma (eg, active lung infection, bronchiectasis, pulmonary fibrosis, cystic fibrosis, hypoventilation syndrome associated with obesity, alpha 1 anti-trypsin deficiency, and primary ciliary dyskinesia) or ever been diagnosed with pulmonary or systemic disease, other than asthma, that are associated with elevated peripheral eosinophil counts (eg, allergic bronchopulmonary aspergillosis/mycosis, eosinophilic granulomatosis with polyangiitis (EGPA), hypereosinophilic syndrome), or prior history of immune complex disease.
- 2 Any disorder, including, but not limited to, cardiovascular, gastrointestinal, hepatic, renal, neurological, musculoskeletal, infectious, endocrine, metabolic, hematological, psychiatric, or major physical impairment that is not stable in the opinion of the Investigator and could:
 - Affect the safety of the participant throughout the study.
 - Influence the findings of the studies or their interpretations.
 - Impede the participant's ability to complete the entire duration of study.
- 3 Life-threatening asthma defined as episodes requiring intubation associated with hypercapnia, respiratory arrest, hypoxic seizures, or asthma-related syncopal episodes.
- 4 History of cancer
 - Participants who have had basal cell carcinoma, localized squamous cell carcinoma of the skin, or in situ carcinoma of the cervix are eligible provided that the participant is in remission and have had their curative therapy completed at least 12 months prior to Visit 1.

- Participants who have had other malignancies are eligible provided that the participant is in remission and have had their curative therapy completed at least 5 years prior to Visit 1.
- 5 Allergy to eggs, if egg based influenza vaccine will be administered.
- 6 History of anaphylaxis to any biologic therapy.
- 7 History of Guillain-Barré syndrome.
- 8 Known or suspected active tuberculosis either treated or untreated.
- 9 A helminth parasitic infection diagnosed within 24 weeks prior to Visit 1 that has not been treated with, or has failed to respond to standard of care therapy.
- 10 Current smokers or participants with smoking history \geq 10 pack-years and participants using vaping products, including electronic cigarettes. Former smokers with a smoking history of < 10 pack-years and users of vaping or e-cigarette products must have stopped for at least 6 months prior to Visit 1 to be eligible.
- 11 History of alcohol or drug abuse within 12 months prior to the date of informed consent.
- 12 Major surgery within 8 weeks prior to Visit 1 or planned surgical procedures during the conduct of the study.

Prior/Concomitant Therapy

- 13 If on allergen immunotherapy, participants must be on a stable maintenance dose and schedule for at least 30 days prior to Visit 1 with no anticipated change in therapy during the conduct of the study.
- 14 Use of immunosuppressive medication (including but not limited to methotrexate, troleandomycin, cyclosporine, azathioprine, tacrolimus, mycofenolate mofetil, intramuscular long-acting depot corticosteroid, or any experimental anti-inflammatory therapy) within 3 months prior to Visit 1.
- 15 Receipt of immunoglobulin or blood products within 30 days prior to Visit 1.
- 16 Receipt of live attenuated vaccines 30 days prior to the date of randomization.
- 17 Receipt of influenza vaccine for season 2021/22 prior to Visit 1.
- 18 COVID-19 vaccination within 6 days prior to randomization.

Prior/Concurrent Clinical Study Experience

- 19 Participants with a known history of allergy or reaction to the study intervention formulations or influenza vaccine.
- 20 Receipt of any marketed or investigational biologic within 16 weeks or 5 half-lives prior to Visit 1, whichever is longer.
- 21 Receipt of any non-biologic investigational medication within 30 days or 5 half-lives prior to randomization, whichever is longer.

- 22 Previously received tezepelumab.
- 23 Concurrent enrollment in another drug-related interventional clinical trial.

Diagnostic Assessments

- 24 Any clinically significant abnormal findings in physical examination, vital signs, baseline ECG, hematology, clinical chemistry, or urinalysis during screening period, which in the opinion of the investigator, may put the participant at risk because of his/her participation in the study, or may influence the results of the study, or the participant's ability to complete entire duration of the study.
- 25 Positive hepatitis B surface antigen, or hepatitis C virus antibody serology, or a positive medical history for hepatitis B or C. Participants with a history of hepatitis B vaccination without history of hepatitis B are allowed to enroll.
- 26 A history of known immunodeficiency disorder including a positive HIV test at V1, or the participant is taking antiretroviral medications as determined by medical history and/or participant's verbal report.
- 27 Positive SARS-Cov2 test during the screening period.
- 28 ALT or AST level \geq 2 times the ULN confirmed during screening period.

Other Exclusions

- 29 For women only - currently pregnant (confirmed with positive pregnancy test), breastfeeding, or lactating women.
- 30 Involvement in the planning and/or conduct of the study (applies to both AstraZeneca staff and/or staff at the study site).
- 31 Employees of the study center or any other individuals involved with the conduct of the study or immediate family members of such individuals.
- 32 Judgment by the investigator that the participant should not participate in the study if the participant is unlikely to comply with study procedures, restrictions, and requirements.

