1.3 Schedule of Activities

Table 1 Schedule of Activities (Screening)

Assessment/activity	Screening		Details in CSP Section or Appendix
Visit	V1 (Week -2 to -3)	V2 ^a (V1 plus maximum 7 days)	
Informed consent/assent	X		Section 5.1
Inclusion and exclusion criteria	X	X	Sections 5.1 and 5.2
Demography	X		Section 5.1
Medical and asthma history ^b	X		Section 5.1
Complete physical examination	X		Section 8.2.1
Weight, height, and BMI	X		Section 8.2.5.2
Vital signs	X	X	Section 8.2.2
Local 12-lead ECG	X		Section 8.2.3
Serum chemistry	X		Section 8.2.4
Hematology	X		Section 8.2.4
Local urinalysis	X		Section 8.2.4
Serum concentration (theophylline) ^c	X		Section 8.2.4
Serology (hepatitis B, C; HIV-1; HIV-2)	X		Section 8.2.5.3
Local SARS-CoV-2 viral diagnostic test ^d	X		Section 8.2.5.4
Serum pregnancy test ^e	X		Section 8.2.5.1
Pre-bronchodilator FEV ₁ ^f	X	X	Section 8.1.2.2
Post-bronchodilator FEV ₁ ^f	X	X	Section 8.1.2.3
Adverse Events	X	X	Section 8.3

Assessment/activity	Screening		Details in CSP Section or Appendix
	Visit	V1 (Week -2 to -3)	
Concomitant medication		X	X

^a Visit 1 and Visit 2 can be combined if the participant has the time and they have not taken SABAs for 6 hours or their long-acting bronchodilator-containing therapy for 12-24 hours. If spirometry/reversibility procedures are actually planned at Visit 1 as a convenience, then the ICF/assent must be signed prior to Visit 1 and prior to instructing the participant to withhold any medication.

^b To include influenza vaccination history.

^c For participants on theophylline, the serum concentration testing will be performed locally.

^d SARS-CoV-2 viral diagnostic test to be performed locally (local COVID-19 viral test).

^e For women of childbearing potential only.

^f Pre and post-bronchodilator spirometry can be done at Visit 1 OR Visit 2. If participants do not demonstrate airway reversibility at either Visit 1 or Visit 2 and this is needed to qualify the participant for randomization, the site should screen fail the participant.

Abbreviations: AE=adverse event; BMI=body mass index; CSP=clinical study protocol; COVID-19=Coronavirus disease 2019; ECG=electrocardiogram; FEV₁=forced expiratory volume in 1 second; HIV=human immunodeficiency virus; ICF=informed consent form; SABA=short-acting β-agonist; SARS-CoV-2= severe acute respiratory syndrome coronavirus 2; V=visit.

Table 2 Schedule of Activities (Randomization, Treatment, and Follow-up)

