5.2.2 At Randomization

Participants are excluded from randomization if any of the following criteria apply:

- 1 Asthma exacerbation during the screening period that requires treatment with oral corticosteroids or a hospitalization/emergency room visit for the treatment of asthma.
- 2 Acute illness or evidence of significant active infection (eg COVID-19) or known influenza infection during the current influenza season.

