6.3.2 Procedures for Handling Incorrectly Enrolled or Randomized Participants

Participants who fail to meet the eligibility criteria should not, under any circumstances, be randomized or receive study intervention. There can be no exceptions to this rule. Participants who are enrolled, but subsequently found not to meet all the eligibility criteria must not be randomized or initiated on treatment and must be withdrawn from the study. These participants are defined as screen failures.

Where a participant does not meet all the eligibility criteria but is randomized in error, or incorrectly started on treatment, the investigator should inform the Parexel Medical Monitor

immediately, and a discussion should occur between the Parexel Medical Monitor and the investigator regarding whether to continue or discontinue the participant from treatment. Study intervention must be discontinued in all cases where continued treatment is deemed to pose a safety risk to the participant and the Parexel Medical Monitor must ensure the decision is appropriately documented. Participants that are discontinued from treatment should be followed up according to the options described in Section 7.1.

In those cases where continuation of the study intervention is judged not to present a concern related to safety and disease management, the rationale for continuing study intervention must be clearly documented.

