Background controller regimen.	Changes are discouraged throughout the study unless judged medically necessary by the investigator or the participant's health care practitioner.
Oral or other systemic corticosteroids or other asthma therapies.	Asthma exacerbations can be treated according to standard practice.

Abbreviations: ICS=inhaled corticosteroids; LABA=long-acting β 2 agonist; LTRA=leukotriene receptor antagonist.

Table 7 Restricted Medications

Type of medication/treatment	Usage
Allergen therapy.	These should not be administered within 7 days of study intervention administration.
Medication with narrow therapeutic range.	The level of theophylline or other drugs with a narrow therapeutic range should not exceed the upper limit of therapeutic range at the time of enrollment.

Table 7 Restricted Medications

Type of medication/treatment	Usage
Scheduled inactivated/killed vaccines, including the COVID-19 vaccination	
These are allowed, provided they are not administered within 6 days before or after study intervention administration.
 
Scheduled influenza vaccination at Visit 6 is not allowed within 6 days after the COVID-19 vaccination.
 
Administration timing of COVID-19 vaccination should be discussed with Parexel Medical Monitor.

Abbreviations: COVID-19= Coronavirus disease 2019; OCS=oral corticosteroids.

Table 8 Prohibited Medications

Type of medication/treatment	Usage
Influenza vaccine.	Not allowed for the fall/winter 2021/22 season prior to randomization or throughout study period (except for the influenza vaccine given at Visit 6 per CSP).
Any immunomodulators or immunosuppressives.	Not allowed 3 months prior to Visit 1, throughout the treatment period or until the End of Study Visit at Week 28 is complete.
Live attenuated vaccines.	Not permitted 30 days prior to randomization, throughout the treatment period or until the End of Study Visit at Week 28 is complete.
Any marketed or investigational biologic product.	Not allowed 16 weeks or 5 half-lives prior to Visit 1, throughout the treatment period or until the End of Study Visit at Week 28 is complete.
Other investigational products (including investigational use of an approved drug).	Not allowed 30 days, or 5 half-lives (whichever is longer), prior to Visit 1, or throughout the treatment period.
Blood products or immunoglobulin therapy.	Not allowed 30 days prior to date of Visit 1 and throughout the treatment period.

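### Exclusion 17 stops at Visit 1 while Table 8 prohibits the season's influenza vaccine up to randomization and beyond, so no specific criterion stops randomization of someone vaccinated during screening

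*Protocol*

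**What the plan says.** **Eligibility.** Protocol Section 5.2.1, exclusion 17, reads "Receipt of influenza vaccine for season 2021/22 prior to Visit 1". The neighbouring vaccine criteria run to randomization instead: exclusion 16 is "Receipt of live attenuated vaccines 30 days prior to the date of randomization" and exclusion 18 is "COVID-19 vaccination within 6 days prior to randomization".

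**At randomization.** Section 5.2.2 has two items. One concerns an asthma exacerbation during screening. The other is "Acute illness or evidence of significant active infection (eg COVID-19) or known influenza infection during the current influenza season". Influenza infection is covered there; influenza vaccination is not.

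**Prohibited medication.** For influenza vaccine, Table 8 in Section 6.5 says "Not allowed for the fall/winter 2021/22 season prior to randomization or throughout study period", with the Visit 6 dose as the only exception.

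**Enforcement.** Section 6.3.2 says "Participants who fail to meet the eligibility criteria should not, under any circumstances, be randomized or receive study intervention". That bar refers to the eligibility criteria, not to Table 8.

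**Timing of the checks.** Section 1.3, Table 1, puts Visit 1 at Week -2 to -3. The medical history item, marked at Visit 1 only, carries the footnote "To include influenza vaccination history". Table 2 has the inclusion and exclusion criteria checked again at Visit 3.

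**Analysis.** The vaccine immunogenicity analysis set (Protocol Table 10, SAP Table 1) leaves out participants with a deviation judged capable of disturbing the antibody response or its interpretation. The study team reviews deviations before unblinding at the primary database lock.

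**The concern.** Two parts of the protocol give different end points for the same restriction. The recheck at Visit 3 does not help as worded, because exclusion 17 still asks only about vaccination before Visit 1.

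The exposure in question is the one that defines the primary endpoints. Every one of them is a Week 16 titer, or its rise from Week 12, after a single study vaccination at Week 12. A participant vaccinated in screening receives a first same-season dose before any tezepelumab or placebo, and a second at Visit 6. Part of the response then cannot show a drug effect. The Week 12 value is no longer a true pre-vaccination value, which bears directly on GMFR and the 4-fold response. It can also carry into the Week 16 GMT and the titer threshold of 40. The ANCOVA adjusts for treatment and age stratum only, so a raised Week 12 titer is not adjusted for in the GMT comparison.

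The event is plausible: Sections 2.1 and 2.2 note that guidelines recommend yearly influenza vaccination for people with asthma.

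**Working it through.** **Step 1: compare the windows for 2021/22 influenza vaccine.**

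| Time of vaccination | Exclusion 17 | Section 5.2.2 | Table 8 |
|---|---|---|---|
| Before Visit 1 | excluded | silent | prohibited |
| Visit 1 to Visit 3 (about 2 to 3 weeks) | not covered | silent | prohibited |
| After randomization, other than Visit 6 | not applicable | not applicable | prohibited |

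Only the middle row shows a conflict: the vaccine is prohibited, but no specific eligibility criterion acts on it.

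**Step 2: reproduce the planned precision.** Inputs from Protocol Section 9.2: 50 per arm, SD 1.2 on the natural log scale, observed ratio 1, 90% CI. The formula is exp(± 1.645 × 1.2 × √(2/n)).

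- n = 50: 1.2 × √(2/50) = 0.240, and 1.645 × 0.240 = 0.395. The interval is 0.674 to 1.484, which matches the stated 0.67 to 1.48.
- A t quantile with 98 degrees of freedom gives 0.671 to 1.490, so the plan used the normal quantile.

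**Step 3: affected participants are removed from the primary set.** The documents give no rate, so these losses are assumptions.

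| Lost per arm | n per arm | 90% CI |
|---|---|---|
| 0 | 50 | 0.674 to 1.484 |
| 2 | 48 | 0.668 to 1.496 |
| 5 | 45 | 0.660 to 1.516 |
| 10 | 40 | 0.643 to 1.555 |

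**Step 4: affected participants are kept.** Suppose a share f of those analysed shows no treatment difference. The expected ratio is then exp((1 − f) × ln R), where R is the true ratio of placebo to tezepelumab. Both f and R = 1.5 are assumptions.

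- f = 2%: 1.488
- f = 5%: 1.470
- f = 10%: 1.440

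The shift is toward 1, which is the less cautious direction in a study looking for impairment. It is small at these shares.

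**The case against.** The strongest reply is that the conduct is already prohibited, likely to be seen, and dealt with in the analysis. Table 8 names the period before randomization, so it applies during screening. Section 6.5 requires any vaccine received to be recorded, and concomitant medication is collected at Visits 1, 2 and 3. Exclusion 32 lets the investigator leave out someone unlikely to comply with restrictions, and inclusion 1 describes consent as something "which includes compliance with the requirements and restrictions listed in the ICF/assent and in this CSP". Exclusions 14, 15 and 20 also run only to Visit 1, with Table 8 governing later use, so exclusion 17 is not alone. The blinded deviation review can then remove the participant from the primary set.

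Much of this stands, and it limits the size of the point. It does not close the gap. Inclusion 1 is a general consent clause and exclusion 32 is discretionary; neither is a vaccine check. The deviation review works only after randomization and case by case. SAP Section 3.3.5 gives prohibited *concomitant* treatment as an example of an important deviation, whereas SAP Section 4.1.8.1 classes a medication that ended on or before the first dose as *prior*. That list of examples is not exhaustive, so a screening-period vaccine can still be caught, but no published rule names it.

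A reader might infer more than the documents support:

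- **That such a participant cannot give a valid primary endpoint.** Both titers can still be measured. The endpoint is compromised, and removal is a matter of judgment.
- **That Table 8 only creates a deviation after randomization.** Its wording covers the period before it.
- **That randomization would be automatic.** The investigator keeps discretion under exclusion 32.
- **That lost participants could not be made up because of the rule in Section 6.3.1.** That rule concerns withdrawal from the study, not removal from an analysis set.
- **That screening took place in autumn.** The documents place study vaccination in fall/winter 2021-2022 at Week 12, which puts Visit 1 about 14 to 15 weeks earlier. Autumn screening is possible but not stated.

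**Conclusion.** The mismatch is real and of minor severity. A participant given the season's vaccine between Visit 1 and Visit 3 breaches Table 8, meets no specific exclusion criterion, and can be randomized with a Week 12 titer that is not a true pre-vaccination value.

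The statistical cost is small. Under assumed losses of 2 to 5 per arm, the upper limit moves from 1.48 to between 1.50 and 1.52. If instead 5% were kept and showed no effect, an assumed true ratio of 1.5 would fall to 1.470. No hypothesis is tested (Protocol Section 9.1), so no decision threshold is crossed.

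It may be tempting to read this as a bias between arms. The vaccination precedes randomization, so it favours neither arm in expectation; what remains is lost precision or dilution toward 1. The documents give no frequency for the event, and the conclusion assumes that cases are few.

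**What to change.** Reconcile exclusion 17 with Table 8, either by ending its window at randomization instead of Visit 1 or by repeating the criterion in Section 5.2.2. The Visit 3 eligibility check would then cover the pre-randomization period that Table 8 already covers.

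If enrollment has closed, name screening-period influenza vaccination in the protocol deviation specification before unblinding, so that removal from the vaccine immunogenicity set follows a rule. That specification is not among the documents and may already do this.

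The cost is one phrase in the protocol and possibly a few more screen failures.
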